18.0 Provisions to Protect the Privacy Interests of Subjects

To protect privacy interests, the personal health information collected for research purposes will be collected from the subject's electronic medical record to limit the amount of people they interact with and provide personal information to.

All interviews will be conducted in a private office or examination room to ensure confidentiality. Phone conversations will be conducted from private offices. Any study correspondence with patients will not indicate disease status or focus on the envelope. All physical exams will be conducted in a private examination room. Subjects will be allowed to skip any question on a questionnaire that makes them feel uncomfortable.

The study staff, including investigators and the study coordinator, will have access to the subject's medical record and study documents. All study documents will be kept in a locked cabinet and only those with password required access to EPIC will be able to access the subject's electronic medical record.

19.0 Compensation for Research-Related Injury

Subjects in need of medical follow-up will be referred to their provider. There will be no compensation for research-related injury.

20.0 Economic Burden to Subjects

Because these patients will already be undergoing retropubic midurethral sling as an inclusion criterion for participation in this study, each participant would already be incurring the costs of visits, parking, all pre-operative and postoperative testing, and operating room fees. There are no additional tests or visits required as part of this study. All onabotulinumtoxinA used and placebo saline in addition to syringes and needles will be covered in the study budget and not incurred by the patient or the patient's insurance.

21.0 Consent Process

Consent will be obtained from the patient by research staff, either by the study coordinator or by one of the investigators. The informed consent process is expected to take up to 30 minutes. The person obtaining consent will verbally go through the form and also allow time for the subject to read the form in its entirety. The subject will be allowed to consult with family. The person obtaining consent will ensure the subject understands the purpose and procedures of the study. After all the subject's questions have been answered, the subject will be given time to make a decision about enrollment. The original signed written consent form will be kept separately from research data at Northwestern, and a signed copy will be given to the patient. We will not be enrolled in our study.

22.0 Process to Document Consent in Writing

We will be following "SOP: Written Documentation of Consent (HRP-091)" and will be documenting process of consent in writing.

23.0 Drugs or Devices

OnabotulinumtoxinA and placebo saline will be stored in the IPHP clinic in a locked cabinet (as is currently done). Once the patient is randomized, the study coordinator will inform the clinic RN who will sterilely prepare the medication and deliver it to the operating room with the patient's study number on the medication, so both the patient and the physician remain masked. Lot number and expiration date will be recorded for each study patient.

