5.0 Study Endpoints

Primary endpoint will occur at 3 months. Secondary endpoint is at 1 year, or when the subject completes her 1 year post-operative visit.

6.0 **Procedures Involved**

Women with MUI undergoing midurethral sling for bothersome SUI will be randomized to 100 units onabotulinumtoxinA or placebo (saline) injections in the detrusor at the time of sling surgery. Specifically, the retropubic midurethral slings used will be either the Gynecare TVT Exact Continence System by Ethicon or the Boston Scientific Advantage Fit Transvaginal Mid-Urethral Sling System based on surgeon preference. Surgeons and participants will be masked to study assignment. Primary outcome will be the Patient Global Assessment of Improvement (PGI-I), a global, patient oriented measure that assesses symptoms of SUI and UUI at 3-months. The primary outcome, PGI-I asks subjects to best describe how their urinary tract condition is now, compared to how it was before treatment for urinary leakage. Response choices are: (1) 'very much better', (2) 'much better', (3) 'a little better', (4) 'no change', (5) 'a little worse', (6) 'much worse', and (7) 'very much worse'. Construct validity of the PGI-I was demonstrated in incontinence trials.32

We selected a subjective, patient oriented outcome as our primary outcome measure secondary to the complex nature of MUI, and the association between dissatisfaction after incontinence surgery and persistent or new onset urgency. We felt the patient's overall impression of their continence status represented a more clinically meaningful outcome than traditional objective measures. In addition, we will compare subjective and objective urinary symptoms and quality of life amongst treatment groups 3-months and 1-year after surgery.

All women with MUI planning surgical intervention with midurethral sling will be approached for study participation. MUI will be defined as an answer of "moderately' or "quite a bit" bothered to Urinary Distress Inventory (UDI) items (2) "urine leakage with a feeling of urgency" AND (3) "urine leakage related to coughing, sneezing, or laughing".

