7.0 Data and Specimen Banking

Data will be collected at Northwestern Medicine. All study data will be recorded on Case Report Forms by research coordinator and securely maintained in a locked cabinet. CRFs will be derived from source documentation and/or participant self-report. Data will be entered by the research coordinator at Northwestern into a REDCap database that will be stored on a secure sever at the Data Coordinating Center. All collected data must be entered into REDCap within 5 business days. Any queries to data entered into REDCap will be addressed by site staff within 5 business days. It is each site's responsibility to regularly check REDCap for data queries.

Both data and specimens will be banked for further use. Patient specimens will not have any directly identifiable patient information on them, but will remain coded for future studies if the specimen is unused in this study. Argonne National Laboratories will have no access to any patient identifying information. All patient identifiers will be removed prior to transferring microbiome samples to Argonne National Laboratories for processing.

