8.0 Data and Specimen Management

All analyses will be conducted using SPSS version 20 (Chicago, IL). Histograms will be used to determine distribution of data and appropriate non-parametric or parametric tests will be selected. Primary outcome will be analyzed dichotomously with responses of "very much better" and "much better" considered an optimal outcome. A chi-square test of association will be used to compare primary outcome (PGI-I) between treatment groups. Questionnaire data will be compared between sling alone and sling plus onabotulinumtoxinA groups using Mann Whitney test. All test results will be considered significant with a p-value of less than or equal to 0.05.

In a study of women with MUI undergoing retropubic midurethral sling, 66% of patients reported a PGI-I of "very much better' or 'much better' at 3-months.23 Similarly, in a randomized trial of intravesical onabotulinumtoxinA 55% of participants had PGI-I scores of "very much better' or 'much better'. Therefore, assuming "optimal outcomes' (PGI-I scores of "very much better' or 'much better' or 'much better) in 66% of women undergoing sling alone and 93% in those undergoing sling plus onabotulinumtoxinA, we will need to recruit 34 patients in each group

to show a significant difference with 80% power at a 0.5 significance level. Assuming a significant attrition rate, we will recruit approximately 100 women (50 in each arm).

Data will be collected at Northwestern Medicine. All study data will be recorded on Case Report Forms by research coordinator and securely maintained in a locked cabinet that only the study coordinator has access to. CRFs will be derived from source documentation and/or participant self-report. Data will be entered by the research coordinator at Northwestern into a REDCap database that will be stored on a secure sever. Only study staff will have passwords to access the project data on REDCap.

The data that is banked locally will be entered into an electronic data capture website. All users of REDCap need an institutional username and password to log in and to enter data. Research personnel, including study staff as well as study doctors will be able to collect and have access to subject data.

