14.0 Setting

Research will be conducted in Northwestern Medical Group's outpatient clinic, the Integrated Pelvic Health Program (IPHP). Potential subjects will be identified and recruited by physicians within the practice. Once potential subjects are identified, the study coordinator will provide the patient with information about the study. If the patient is interested in joining the study, the study coordinator will consent the patient in the IPHP clinic. The patients will complete questionnaires per the study either at home or in the clinic in a private room. Demographic and medical and surgical data will be collected from the patient's medical record and recorded on the RedCAP secure server. $PROTOCOL \ TITLE: \ \text{The SLIM Study: } \underline{Sl} \text{ing and Botox} \\ \textcircled{B} \ \underline{Injection for } \underline{M} \text{ixed Urinary Incontinence}$

After consenting to the study, the surgical procedure that subjects are undergoing as part of their standard of care will be performed at an NMHC facility. The onabotulinumtoxinA injections will be performed in the operating room by one of the study physicians. Randomization will be performed via RedCAP on a secure online server through a hospital computer.

The subjects post-operative visits will take place in the Integrated Pelvic Health program, and NMHC outpatient clinic, as part of standard of care. Additional questionnaires will be completed at these visits and data will be collected from these visits as well.

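### As the drug-preparation step is written, the coordinator who records the trial's data, including adverse events, appears to know the treatment arm

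*Protocol*

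**What the plan says.** Protocol section 23.0 (Drugs or Devices) describes how study drug reaches the operating room: "Once the patient is randomized, the study coordinator will inform the clinic RN who will sterilely prepare the medication". The syringe is labelled with the study number, "so both the patient and the physician remain masked". The section adds: "Lot number and expiration date will be recorded for each study patient". It does not say who keeps that record.

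Section 6.0 (Procedures Involved) states the masking as: "Surgeons and participants will be masked to study assignment". Section 14.0 (Setting) says: "Randomization will be performed via RedCAP on a secure online server through a hospital computer". It does not say who runs the randomization or who sees the result.

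On data handling, section 7.0 says: "All study data will be recorded on Case Report Forms by research coordinator". The same role enters the data in REDCap. Section 7.0 also says: "CRFs will be derived from source documentation and/or participant self-report". Section 8.0 repeats the arrangement and describes the forms as "securely maintained in a locked cabinet that only the study coordinator has access to". Section 9.0 has adverse events recorded on the CRFs at each follow-up visit.

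The SAP does not mention masking of the coordinator, of adverse event recorders or of the analyst.

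**The concern.** In a double-blind trial, the people who record outcomes and harms should be masked as well as patients and surgeons. Here one role appears to sit on both sides: it passes the allocation to the nurse and then records the trial's data.

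What is at stake is the description of adverse events by arm. Section 9.0 lists three types: retention requiring catheterization, urinary tract infection, and persistent urinary urgency. A recorder who knows the arm could, without intending to, ask about or classify urgency differently in the two groups. Section 9.0 gives no definition of persistent urgency that would limit this. Section 11.0 gives retention, with the infection risk that follows from it, as the added risk of the injection. Readers will therefore weigh the adverse event profile by arm against any benefit.

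**Working it through.** No figure in the plan bears on this point, so there is nothing to recompute. The check sets the relevant statements side by side.

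1. **Does the coordinator learn the arm?** The nurse prepares either active drug or saline, so the nurse must know which. Section 23.0 gives one route by which the nurse is told anything: the coordinator. Section 14.0 places randomization in REDCap but assigns the result to nobody. No passage has the nurse look up the allocation. The natural reading is that the coordinator sees the arm and passes it on. This is an inference, because section 23.0 does not say what the nurse is told.

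2. **Is this the person who records the data?** Section 7.0 assigns the CRFs to the research coordinator. Section 8.0 uses research coordinator and study coordinator in one sentence about the same forms, and gives only the study coordinator access to the cabinet. Section 15.0 describes one study coordinator on staff. The two titles therefore appear to mean one role.

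3. **Does that role record adverse events?** Section 7.0 covers all study data, and section 9.0 puts adverse events on the CRFs. Section 6.0 says that research staff record them. Section 21.0 uses that term for the study coordinator or an investigator. The coordinator is thus included, though not exclusively.

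4. **Is anyone beyond patient and physician stated to be masked?** No. Sections 6.0 and 23.0 name the same two groups. The coordinator, the nurse, the clinical staff who assess adverse outcomes at visits, and the analyst are not mentioned. The SAP says the analysed data were de-identified, which is not the same as masked to arm.

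5. **Are there other routes to the allocation?** Two are left open. A product lot number recorded for each patient could reveal the arm, and the record has no named keeper. Section 8.0 gives study staff and study doctors access to subject data in REDCap, which also performs the randomization. No limit on viewing allocation is stated.

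6. **Which results are exposed?**
   - PGI-I, UDI, IIQ, PGI-S and the 3-day diary: completed by masked participants, so little exposed.
   - Retention requiring catheterization and urinary tract infection: more likely to have a source document, so less exposed.
   - Persistent urinary urgency: rests mainly on judgement, so most exposed.

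**The case against.** The strongest reply is that two inferences are needed. First, the coordinator may tell the nurse only that a patient has been randomized, and the nurse may then read the arm in REDCap. Second, recording an event on a CRF is not the same as deciding that it occurred. CRFs come from source documents and/or self-report, section 2.0 has follow-up visits with a physician, and section 6.0 has clinical staff assess adverse outcomes. The coordinator may simply transcribe. In addition, the UDI and diary capture urgency leakage independently, and neither section 8.0 nor the SAP names a between-arm test of adverse events. On this view one clarifying sentence would be enough.

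Much of this stands and limits the point. The first inference is not proved, the efficacy measures are protected, and a skewed record of urgency could be checked in part against the UDI and diary, although not for urgency without leakage. Two parts do not remove the concern. The protocol nowhere describes the nurse reading the allocation, and if that is the practice, the lot record and REDCap access still need closing. The clinical staff at visits are not stated to be masked, and nothing keeps the nurse who prepared the syringe from being one of them.

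**Conclusion.** The concern holds. On the natural reading of section 23.0, the main data recorder knows the arm, and the plan does nothing to prevent it. This does not contradict the double-blind label, which the protocol supports for participants and surgeons. It is an avoidable exposure that the described workflow leaves open.

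The efficacy comparison is little affected. The risk lies in an unbiased description of adverse events by arm, chiefly one of the three listed types. The size of any bias cannot be calculated from the documents.

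The conclusion assumes that informing the nurse includes stating the arm, and that the research coordinator and study coordinator are the same role. Confidence is medium. The change should be made because it is cheap. If the coordinator is in practice already masked, the amendment simply documents that.

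**What to change.** Amend section 23.0, and section 14.0 to match:

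- The nurse who prepares the syringe reads the allocation directly from REDCap. The coordinator gives that nurse only the study number and surgery date.
- That nurse keeps the lot number and expiration log where the coordinator and physicians cannot open it.
- The coordinator and all other recorders of outcomes or adverse events have no REDCap right to view allocation and stay masked until database lock.
- The preparing nurse records no trial outcomes or adverse events.

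The cost is a few sentences of protocol text, one REDCap login and one user-rights setting. This assumes that the REDCap set-up, which the documents do not describe, allows allocation to be hidden by user. The downside is that one unmasked nurse remains in the clinic where follow-up takes place, so some of that nurse's visit tasks may have to be reassigned. The current plan already has an unmasked nurse, so the amendment does not create that exposure.

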## Statistical Analysis Plan

We based the sample size estimation off of previous studies assessing treatment of slings for mixed urinary incontinence and onabotulinumtoxinA injections for overactive bladder. A PGI-I response at 3 months postoperatively of "very much better" or "much better" was designated "improved." Assuming 66% of women in the placebo group and 93% in the onabotulinumtoxinA group were "improved" based on overall PGI-I scores, 68 women (34 in each arm) were needed to show a significant difference with 80% power at 0.05 significance level. If we assumed a 15% dropout rate, we aimed to recruit 78 participants (39 in each arm). R 3.6.3 was used for statistical analysis of the deidentified data. Independent samples t test, Mann-Whitney, x2, Wilcoxon signed rank sum statistical tests were used as appropriate.

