15.0 Resources Available

The staff that will be involved in this research are highly qualified. The Principle Investigator, [name], is the chief of Female Pelvic Medicine and Reconstructive Surgery and is nationally and internationally recognized for research in pelvic floor disorders and has served as primary investigator on many studies funded by the National Institute of Health. She has authored or coauthored 150 scientific papers and currently serves on the editorial board of Obstetrics & Gynecology and the Journal of Female Pelvic Medicine & Reconstructive Surgery. The other study physicians assisting in recruiting efforts have completed their fellowships in Female Pelvic Medicine & Reconstructive surgery and are both involved in numerous research studies and serve as reviewers for several scientific journals. The nurse practitioner on staff at the IPHP has worked on several other protocols during her time at Northwestern. The study coordinator on staff has over 3 years of research experience and 1 year of experience working in clinical trials and consenting patients.

Due to the high volume of patients that present with mixed urinary incontinence in our clinic, it is feasible that the required number of suitable subjects will be recruited within the estimated window of time. Also, since study participants are undergoing surgery as part of standard of care, they will be more likely to return for their follow-up visits since these are part of their standard post-operative care. Our center will begin enrolling participants once we have IRB approval, tentatively July 2015. With the time required recruit 100 patients (approximately two years), collect outcomes data on the enrolled subjects for a year, and analyze data, this study will be active until June 2018.

The Integrated Pelvic Health Program, affiliated with Northwestern Memorial Hospital, helps individuals with pelvic floor disorders. It is the only program in the Chicago area that brings together a multispecialty approach to pelvic floor disorders in one location. Our dedicated team of physicians, nurses, and physical therapists are committed to restoring the quality of life for people with such disorders. Both the physicians and the facilities offer state-of-the-art resources to ensure the highest quality evaluation, medical and surgical care to women with incontinence and prolapsed. Our physicians are national leaders in minimally

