17.0 Local Number of Subjects

This is a single center study at Northwestern Medicine. We will require up to 100 participants to meet power requirements for this study while appropriately accounting for attrition rate.

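### The SAP's recruitment target of 78 leaves about 66 evaluable women at its own 15% dropout, not the 68 it needs, and the change from the protocol's target of about 100 is not explained

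*SAP*

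**What the plan says.** Both documents assume the same improvement rates on the PGI-I at 3 months and the same evaluable number.

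- **SAP, Statistical Analysis Plan:** "68 women (34 in each arm) were needed to show a significant difference with 80% power at 0.05 significance level". It then sets the recruitment target: "If we assumed a 15% dropout rate, we aimed to recruit 78 participants (39 in each arm".
- **Protocol 8.0:** optimal outcomes are assumed "in 66% of women undergoing sling alone and 93% in those undergoing sling plus onabotulinumtoxinA", and from this "we will need to recruit 34 patients in each group". Recruitment is then set higher: "Assuming a significant attrition rate, we will recruit approximately 100 women (50 in each arm". No attrition percentage is given.
- **Protocol 15.0** builds the enrolment timeline on the same figure: "With the time required recruit 100 patients (approximately two years".
- **Protocol 17.0** gives it as a ceiling: "We will require up to 100 participants to meet power requirements for this study while appropriately accounting for attrition rate".

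The significance level in the sample-size sentence of protocol 8.0 is printed as 0.5. The testing criterion in the same section, and the SAP, both use 0.05.

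**The concern.** Two things do not fit.

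1. Within the SAP, the evaluable number, the dropout rate and the recruitment target should be linked by simple arithmetic, and they are not. If 15% of 78 women are lost, fewer than 68 remain.
2. Across the documents, the same 34 per arm leads to about 100 recruits in one place and 78 in the other. As the assumed rates and the evaluable number agree, only the attrition allowance can account for the difference, and the protocol never states it.

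At stake is the accuracy of the sample-size record. A reader should be able to get from the evaluable number to the recruitment target, and to see why the target fell by 22 women.

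**Working it through.** **Inputs.** Improved rates p1 = 0.66 and p2 = 0.93, 80% power and significance level 0.05 (SAP; same rates and power in protocol 8.0). Chi-square test (protocol 8.0). Dropout 15% and target 78 (SAP). Target about 100 (protocol 8.0, 15.0, 17.0). Sidedness is not stated; two-sided is assumed, the ordinary reading of a 2 × 2 chi-square test.

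**Step 1: reproduce 34 per arm.** The pooled-variance formula without continuity correction, with mean rate p = (0.66 + 0.93)/2 = 0.795, is

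n = [1.960 × √(2p(1 − p)) + 0.842 × √(p1(1 − p1) + p2(1 − p2))]² / (p2 − p1)²

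- First term: 1.960 × √0.32595 = 1.119
- Second term: 0.842 × √(0.2244 + 0.0651) = 0.453
- n = (1.119 + 0.453)² / 0.27² = 33.9, so **34 per arm, 68 in total**

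This matches both documents. The unpooled and arcsine versions give 32 per arm, and a continuity correction gives 41. The uncorrected pooled formula is therefore taken as the planning formula.

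**Step 2: apply the SAP's dropout to its own target.**

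- Women remaining: 78 × (1 − 0.15) = 66.3, or 39 × 0.85 = 33.15 per arm
- Recruits needed to retain 68: 68 / 0.85 = 80 (40 per arm)
- Largest dropout at which 78 still leaves 68: 1 − 68/78 = 12.8%
- For comparison, 68 × 1.15 = 78.2. The SAP's 78 is what results from adding 15% to 68 instead of dividing by 0.85. The SAP names no formula, so this is a probable origin only.

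**Step 3: effect on power at 66% against 93%.**

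| Evaluable per arm | Planning formula | Exact, uncorrected chi-square |
|---|---|---|
| 33 (from 78 at 15%) | 78.9% | 82.0% |
| 34 (from 80 at 15%) | 80.1% | 83.3% |

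The loss is about one percentage point by either method.

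**Step 4: compare the two targets.** Both documents want 34 per arm. For 100 recruits to end at 68, attrition would be 1 − 68/100 = 32%. The SAP's stated rate is 15%. The targets differ by 100 − 78 = 22 women.

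**The case against.** The strongest reply is that nothing of substance is lost. The gap between 78 and 80 is two women, and exact power of the chi-square test at 33 per arm is 82%, above the stated 80%. The SAP is written in the past tense, while the protocol looks ahead to enrolment starting tentatively in July 2015. The natural reading is that the SAP records the later target, and 78 lies within protocol 17.0's ceiling of 100.

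Most of this stands, and it limits the point in three ways.

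- A reader might infer that the trial was underpowered. The figures do not support that: the planning formula gives 79%, and the exact calculation stays above 80%.
- A reader might apply the SAP's 15% to the protocol's 100, get 85 evaluable women, and conclude that designed power was cut when the target fell to 78. The protocol never assumes 15%. Both documents design for the same 34 per arm, so what differs is the attrition allowance and not the designed power.
- A reader might say that the governing target cannot be known. That goes too far, given the tense of the two documents.

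Two things remain. The SAP's 78 does not follow from its own 68 and 15%, however small the consequence. And no reason is given for the lower target: protocol 8.0 and 15.0 plan on about 100 or 100, not merely on a ceiling.

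**Conclusion.** The point holds as a minor correction to a figure that is wrong as written. The 34 per arm is correct. At 15% dropout the SAP's 78 leaves about 66 evaluable women (33 per arm) against 68 needed, at a cost of about one point of power. The difference between about 100 in the protocol and 78 in the SAP is an unexplained change in the attrition allowance, from an unquantified rate (about 32% if the trial is to end at 68) to 15%.

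This rests on a two-sided test, an uncorrected chi-square, the documents' 66% and 93%, and dropout spread evenly over the arms. The printed 0.5 is clerical and has no bearing on the sample size.

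**What to change.** No added enrolment and no change to trial conduct.

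1. In the SAP, do one of the following: give 80 as the figure that matches 68 evaluable at 15% dropout; keep 78 and state that it yields about 66 evaluable women (33 per arm); or keep 78 and state that it covers dropout up to 12.8%. If power is restated for 33 per arm, name the method: 79% by the planning formula, 82% by exact enumeration. Printing 79% alone would suggest a shortfall below 80% that the exact test does not show.
2. Add one sentence saying when and why the recruitment target and attrition allowance changed from about 100 to 78.
3. In protocol 8.0, correct the printed significance level from 0.5 to 0.05.

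The cost is a few sentences. As the SAP is written in the past tense, this corrects the record.
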